- Treatment will be definitely discontinued upon patient's request, or in case of disease progression, intolerable toxicity, treatment interruption > 2 weeks due to toxicity (except in case of suspicion of hematological DLT in acute leukemia, where treatment interruption for 3 weeks is allowed to confirm DLT), recurrence of the same toxicity despite dose reduction, specific liver toxicities (see Dose and Schedule Adaptation below), lack of compliance, or major protocol deviation.
- Dosing not performed at the same time $(\pm 2 \text{ hours})$ as the other days will be omitted.
- Omitted or vomited doses will not be replaced.

The recommended dose (RD) for expansion cohorts for both acute leukemia and other hematologic malignancies is 80 mg QD days 1 to 14 of 21-day cycles (2 weeks ON/one week OFF)

Dose & schedule adaptation

Study product dosing (OTX015/MK-8628) will be interrupted in case of: Non-hematological toxicities:

- any grade 3-4 non hematological toxicity despite adequate medication, regardless of duration;
- grade 3-4 asymptomatic non hematological laboratory abnormal values, deemed related to study medication, lasting > 7 days. This definition applies for patients with lab values grade ≤ 1 at baseline. For patients with grade 2 values at baseline, only grade 4 lasting > 7 days will be considered DLT, unless the SMC considers the event clinically significant. See below for liver function tests.
- Any prolonged grade 2 toxicity (lasting more than 2 weeks), leading to treatment interruption and/or dose reduction.

Hematological toxicities:

-- Patients with acute leukemia:

- pancytopenia with a hypocellular bone marrow and no marrow blasts lasting for ≥ 6 weeks after the start of a cycle.
- Patients with other hematological malignancies:
 - any grade 3 neutropenia, with fever or infection; any grade 3 thrombocytopenia with bleeding,
 - any grade 4 neutropenia or thrombocytopenia, lasting \geq 3 days.

OTX015/MK-8628 dosing will be resumed when all toxic events have resolved to grade ≤ 1 (or to the baseline value) at a reduced dose : at the DL immediately below during the dose escalation phase.

During the cohort expansion phase, patients initially treated at 80 mg will have their dose reduced to 60 mg QD (2 weeks ON/1 week OFF) at the first occurrence of toxicity, then to 40 mg QD (2 weeks ON/1 week OFF) if the same toxicity recurs.

In all cases

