• Dosing interruption for > 2 weeks due to toxicity, recurrence of the same toxicity with the same severity despite one dose reduction, or specific liver toxicities* will lead to definitive study treatment discontinuation, unless the investigator thinks the patient's best interest is to pursue study treatment, with sponsor's agreement.

* Any of the following liver test abnormalities** (see Appendix 16.12)

- ALT or $AST > 8 \times ULN$
- ALT or $AST > 5 \times ULN$ for > 2 weeks
- ALT or AST > 3 x ULN AND (total bilirubin > 2 x ULN OR INR > 1.5)

ALT or AST > 3 x ULN with the appearance of fatigue, nausea, vomiting, right upper quadrant pain or tenderness, fever, rash and/or eosinophilia (> 5%), unless the investigator assesses the rash or fatigue to be related to OTX015 and not related to liver impairment with sponsor's agreement.

**Note: All patients with these liver test abnormalities should be monitored weekly until all abnormalities return to normal or to the baseline state. For patients with isolated total bilirubin increases >2 x ULN or 2 x baseline (if elevated at baseline), except if associated with direct bilirubin \leq ULN, monitoring should be every 2 weeks until bilirubin returns to normal or to the baseline state. Drug induced liver injury (DILI) may develop or progress even after the causative drug has been stopped. Results should be recorded on the CRF and in the database. See guidelines on the handling of these events (potential Hy's law cases).

Premedication

No premedication is planned at the first cycle, in the first 3 patients. Decision of further systematic premedication should be taken by the SMC.

Dose escalation scheme:

• The starting dose will be 10 mg/day (once a day, flat dose, without adaptation for body weight or surface area),

• DLTs will be collected during the first cycle (21 days after the first OTX015/MK-8628 administration) The dose escalation scheme will be as follows for each subset (AL and other hematological malignancies). The magnitude of dose escalation between two consecutive dose levels will depend upon the occurrence or not of DLT at the current DL.

Dose Level					
1 (starting dose) (mg)	10				
2	20				
3	30	40			
4	40	60	80		
5	50	80	120		
Dose escalation schedule:					
Doubling the dose in the absence of DLT (grey boxes).					
Fibonacci-lik	te model once at least one D	DLT occurs (white boxes)			

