5.2.4.2 Dose adaptation

Study product dosing (OTX015/MK-8628) will be interrupted in the event of AEs corresponding to the definition of a DLT (see section 3.2), but regardless of the cycle in which they occur:

Non hematological toxicity

- Any grade 3 or 4 non-hematological event (regardless of duration), unless it was not optimally treated with supportive care (e.g. grade 3 vomiting not adequately treated according to antiemetic standard of care).
- Grade 3-4 asymptomatic laboratory abnormal values lasting > 7 days. This definition applies for patients with lab values grade ≤ 1 at baseline. For patients with grade 2 values at baseline, only grade 4 lasting > 7 days will be considered DLT, unless the SMC considers the event clinically significant. See below for liver function tests*.

- Any prolonged grade 2 toxicity (lasting more than 2 weeks) leading to treatment interruption and/or dose reduction.
- * Any of the following liver test abnormalities** (see Appendix 16.12)
 - ALT or $AST > 8 \times ULN$
 - ALT or AST $> 5 \times ULN$ for > 2 weeks
 - ALT or AST > 3 x ULN AND (total bilirubin > 2 x ULN OR INR > 1.5)
 - ALT or AST > 3 x ULN with the appearance of fatigue, nausea, vomiting, right upper quadrant pain or tenderness, fever, rash and/or eosinophilia (> 5%), unless the investigator assesses the rash or fatigue to be related to OTX015 and not related to liver impairment with sponsor's agreement.

**Note: All patients with these liver test abnormalities should be monitored weekly until all abnormalities return to normal or to the baseline state. For patients with isolated total bilirubin increases >2 x ULN or 2 x baseline (if elevated at baseline), except if associated with direct bilirubin \leq ULN, monitoring should be every 2 weeks until bilirubin returns to normal or to the baseline state. Drug induced liver injury (DILI) may develop or progress even after the causative drug has been stopped. Results should be recorded on the CRF and in the database. See guidelines on the handling of these events (potential Hy's law cases).

Hematological toxicity

Patients with AL

• Pancytopenia with a hypocellular bone marrow and no marrow blasts lasting for ≥ 6 weeks after the start of a cycle.

Patients with other hematological malignancies

- Any grade 3 neutropenia, with fever or infection
- Any grade 3 thrombocytopenia with bleeding,
- Any grade 4 neutropenia or thrombocytopenia, regardless of symptoms and lasting \geq 3 days.

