OTX015/MK-8628 dosing will be resumed when all toxic events have resolved to grade < 2 (or baseline value).

• At reduced dose :

- During the dose escalation, at the DL immediately below.

- During expansion cohorts, patients treated at 80mg QD (2 weeks ON/ 1 week OFF) will have their dose first reduced to 60mg QD (2 weeks ON/ 1 week OFF), then to 40mg QD (2 weeks ON/ 1 week OFF), should the same toxicity recurs.

• Dosing interruption for > 2 weeks due to toxicity will lead to definitive study treatment discontinuation, unless the investigator thinks the patient's best interest is to pursue study treatment.

• If the same DLT is observed again after dose reduction, the study treatment should be definitely discontinued, unless the investigator thinks the patient's best interest is to pursue study treatment with further dose reduction, with sponsor's agreement.

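### Protocol 5.2.4.2 resumes dosing by default after a listed liver-test event resolves, while 5.3, section 9 and the synopsis stop treatment by default for the same event

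*Protocol*

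**What the plan says.** Section 5.2.4.2 opens with the rule that "Study product dosing (OTX015/MK-8628) will be interrupted in the event of AEs corresponding to the definition of a DLT", in whichever cycle they occur. Among those events it places a list headed "Any of the following liver test abnormalities (see Appendix 16.12"), with four criteria:

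1. ALT or AST > 8 × ULN
2. ALT or AST > 5 × ULN for > 2 weeks
3. ALT or AST > 3 × ULN with total bilirubin > 2 × ULN or INR > 1.5
4. ALT or AST > 3 × ULN with symptoms such as nausea, fever or rash (with a carve-out for rash or fatigue attributed to the drug itself)

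A note on liver monitoring ends with "See guidelines on the handling of these events". The section then gives the resumption rule: "dosing will be resumed when all toxic events have resolved to grade < 2 (or baseline value"), at a reduced dose. It attaches two routes to a permanent stop. One is "Dosing interruption for > 2 weeks due to toxicity will lead to definitive study treatment discontinuation", which the investigator may override alone. The other is recurrence of the same DLT after reduction, which may be overridden with the sponsor's agreement. Neither mentions the liver list.

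Section 5.3 names the same four criteria as points at which treatment ends. Section 9, item 7, does so again among the reasons for definite discontinuation. The synopsis, under Treatment, includes among its reasons for stopping "specific liver toxicities (see Dose and Schedule Adaptation below), lack of compliance, or major protocol deviation". Under Dose & schedule adaptation it has its own resumption sentence, "dosing will be resumed when all toxic events have resolved to grade ≤ 1 (or to the baseline value) at a reduced dose", and then says that "specific liver toxicities* will lead to definitive study treatment discontinuation, unless the investigator thinks" continuing serves the patient and the sponsor agrees.

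**The concern.** An investigator managing a toxicity will look first in the section on dose adaptation. Followed as written, that section returns a patient to the drug after a liver event that other sections treat as a reason to leave treatment.

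The liver is not a minor organ for this compound. Section 1.1.4 identifies the digestive system, and the liver in particular, as the main site of toxicity in the animal studies. The note in 5.2.4.2 itself warns that drug-induced liver injury can progress after the drug is withdrawn. That note also keeps weekly liver monitoring going until values are normal or back to baseline, whereas resumption needs only a grade below 2. Re-dosing could therefore begin before the protocol's own liver follow-up has ended.

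**Working it through.** No sample size, power or event count is involved, so the check is a comparison of texts.

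**Default action after a listed liver event that has resolved**

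| Place | Default | Exception |
|---|---|---|
| 5.2.4.2 | Resume at a reduced dose | None for the liver list |
| 5.3 | Treatment ends | None |
| Section 9, item 7 | Discontinue | None in item 7 (items 3 and 4 have one), but the list sits under the investigator's opinion on benefit and risk |
| Synopsis, Dose & schedule adaptation | Discontinue | Investigator's judgement plus sponsor's agreement |

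**Stop conditions attached to the resumption rule.** The synopsis has three: interruption > 2 weeks, recurrence after reduction, and specific liver toxicities. Section 5.2.4.2 has two. The difference is 3 − 2 = 1, and the missing one is liver.

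**What Appendix XII adds.** Its advice to stop applies when ALT or AST is ≥ 3 × ULN, bilirubin is ≥ 2 × ULN and ALP is < 2 × ULN, all together. Against the four criteria:

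- Criterion 1 (> 8 × ULN): not covered unless bilirubin is also raised.
- Criterion 2 (> 5 × ULN for > 2 weeks): not covered on its own. The duration makes it likely that the > 2-week interruption rule in 5.2.4.2 applies as well, so the gap is less clear.
- Criterion 3 (with bilirubin or INR): the bilirubin form is covered when ALP is < 2 × ULN, and the note in section 8.3 also directs the INR form to the appendix. The conflict in wording remains but is softened.
- Criterion 4 (> 3 × ULN with symptoms): not covered when bilirubin is not raised.

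Criteria 1 and 4 therefore leave the clearest gap.

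**A worked case.** Take a first episode of ALT above 8 × ULN, bilirubin normal, with all toxicity back to baseline after 10 days.

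- 10 days is less than 14, so the > 2-week rule in 5.2.4.2 is not triggered.
- It is a first event, so the recurrence rule is not triggered.
- Appendix XII's laboratory criteria are not met.
- Result under 5.2.4.2: resume at a reduced dose, with no sponsor agreement required.
- Result under 5.3: treatment ends. Under section 9: discontinue. Under the synopsis: discontinue unless the sponsor agrees otherwise.

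**Effect on the primary endpoint.** The same liver criteria are DLTs under section 3.2.1 when they occur in cycle 1, and a patient with a DLT is evaluable whatever dose was received (section 11.2). Whether dosing later resumes changes neither the count nor the denominator.

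**The case against.** The best defence is that the sections can be read together. Interrupting on detection is compatible with then discontinuing. On this view 5.2.4.2 is the general rule for patients who stay on treatment, while 5.3 and section 9 decide who leaves it. The liver list in 5.2.4.2 refers to Appendix XII. After its advice to stop, the appendix sends the reader to the protocol's specific discontinuation criteria. Section 8.3 requires a report to the sponsor within 24 hours for all four criteria, and weekly liver monitoring applies.

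Part of this stands. A reader might infer that the documents give no direction at all on which section prevails. The appendix sentence is a pointer towards stopping, so that goes too far. But the pointer is indirect and follows text on the appendix's own laboratory criteria. Section 5.2.4.2 reproduces the full liver list, so it is no less specific than 5.3, and it contains neither an exception nor a reference to 5.3 or section 9. The 24-hour report informs the sponsor; it does not decide on resumption.

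A reader might also infer a clean opposition between re-dosing and an absolute permanent stop. That is not supported either: the synopsis permits continuation with sponsor agreement, and section 9 introduces its list through the investigator's opinion. The conflict is between defaults.

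Finally, the SAP's copy of the synopsis also lacks the liver stop condition, which might suggest that it was added to the protocol later and not carried into 5.2.4.2. The SAP copy omits the liver items elsewhere too, so this proves nothing about 5.2.4.2.

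**Conclusion.** The point holds as a conflict of default actions. For ALT or AST > 8 × ULN, or > 3 × ULN with symptoms and no bilirubin rise, resolving within 2 weeks, 5.2.4.2 re-doses without sponsor agreement, while 5.3, section 9 and the synopsis stop by default. It should be fixed on patient-safety grounds.

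Its size is one decision per affected patient: resume at a reduced dose, or stop. How many patients that concerns cannot be derived, because the documents give neither the frequency of such events nor the number of patients dosed while this text applied. Enrolment totals and the time left to the planned end of enrolment do not measure it. A reader might infer that the recommended dose is in doubt; it is not, since DLT counts do not change. Tables of discontinuation and exposure would differ only descriptively.

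The conclusion assumes that an investigator applies 5.2.4.2 as written, without consulting 5.3 or section 9.

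**What to change.** In 5.2.4.2, directly after the resumption sentence, add: *except for the four liver-test abnormalities listed above, which lead to definitive discontinuation per sections 5.3 and 9*. In the synopsis, under Dose & schedule adaptation, take the liver item out of the override so that all sections agree.

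If the sponsor prefers to keep the override, changing 5.2.4.2 alone would leave it in conflict with 5.3. The same wording (stop by default; resume only with the sponsor's agreement) then has to go into the synopsis, 5.2.4.2, 5.3 and section 9.

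The cost is one sentence and one deletion, or matching wording in four places. No visits, samples or analyses are added. SAP section 5 reports the study as completed, so the correction serves any reuse of this text. The sponsor can also check the planned listings of dose modifications and worsening biochemistry for any patient re-dosed after a listed liver event.

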5.2.5 Supportive care guidelines in case of study treatment toxicity

Toxicity will be managed by the investigators according to local standard of care.

Supportive treatment of toxicities should be reported in the concomitant medication section of the case report form (CRF).

Handling of hepatotoxicity for potential DILI will be managed according to the treatment guidelines outlined in Appendix 16.12.

5.3 TREATMENT DURATION

Treatment will be continued until:

- Disease progression
- Intolerable toxicity
- Treatment interruption for > 2 weeks due to toxicity (except in case of suspicion hematological DLT in acute leukemia, where treatment interruption for 3 weeks is allowed to confirm DLT)
- Recurrence of DLT despite dose reduction.
- Any of the following liver test abnormalities (see Appendix 16.12)
 - ALT or $AST > 8 \times ULN$
 - ALT or AST $> 5 \times ULN$ for > 2 weeks
 - ALT or AST > 3 x ULN and (total bilirubin > 2 x ULN OR INR > 1.5)
 - ALT or AST > 3 x ULN with the appearance of fatigue, nausea, vomiting, right upper quadrant pain or tenderness, fever, rash and/or eosinophilia (> 5%), unless the investigator assesses the rash or fatigue to be related to OTX015 and not related to liver impairment with sponsor's agreement
- Patient's request (consent withdrawal).

5.4 TREATMENT ASSIGNMENT

The investigational product will be administered only to subjects included in this study following the screening procedures set out in the clinical study protocol.

All patients must be registered prior to the start of treatment. A patient, who has not been registered before the first treatment administration, will not be accepted for the study at a later date.

After verifying that the patient meets eligibility criteria and has signed the Informed Consent Form, the investigator will request the patients' registration number by faxing/e-mailing the Patient's Registration Form to:

C C C C C C C C C C C C C C C C C C C
Study project leader, Oncology Therapeutic Development (OTD)
Fax :
Mobile : PPD
E-mail:

The Patient's Registration Form will (see Appendix III, section 16.3) contain the following information necessary to determine eligibility:

- 1. Institution name,
- 2. Sender's name,
- 3. Principal investigator's name,
- 4. Patient's identification (first letter of first, middle and last name),
- 5. Patient's age and gender
- 6. Performance status,
- 7. Planned date of treatment,
- 8. Date when informed consent obtained.
- 9. Verification of selected inclusion and exclusion criteria with values of the hematological, and biochemical results and dates of all the examinations performed,
- 10. Prior anticancer therapies and dates of last therapies
- 11. Co-morbidities
- 12. Tumor-related symptoms present at screening.
- 13. In- or outpatient

After validation and signature by the Sponsor's Medical Monitor, the registration form will be returned to the investigators, with or without inclusion agreement. Any inclusion refusal will be motivated on the inclusion form. In case of inclusion, a unique patient number (UPN) will be assigned to the patient and reported on the inclusion form.

The UPN will consist of 3 to 5 digits (1 or 2 for the center and 2 or 3 for the patient, by increasing order of inclusion) and will be recorded in the case report form (CRF).

The dose level allocated, and the schedule of administration will be specified on the form.

A patient should be included and therefore will receive a UPN only when the patient is about to start the treatment. Anyway, the treatment must begin within 7 days after registration.

Subjects withdrawn from the study retain their UPN. New subjects must always be allotted a new UPN.

5.5 PACKAGING AND LABELING

The investigational product is supplied as size 3 gelatin capsules containing 10 mg or 20 mg of OTX015/MK-8628 or size 0 gelatin capsules containing 40 mg of OTX015/MK-8628.

OTX015/MK-8628 will be supplied in bottles of 21 capsules. Clinical supplies will be affixed with a clinical label in accordance with regulatory requirements.

5.6 CAPSULE STRENGTHS

OTX015/MK-8628 will be provided as capsules with strengths of 10 mg, 20 mg and 40 mg of active compound.

5.7 SUPPLIES AND ACCOUNTABILITY

The pharmacist of the investigational center will inventory and acknowledge receipt of all shipments of the investigational medicinal product. The investigational product must be kept in a locked area with restricted access. The investigational product must be stored and handled in accordance with the manufacturer's instructions. Traceability of the temperature will be required. The pharmacist will also keep accurate records of the quantities of the investigational product dispensed, used, and returned by each subject. The study monitor will periodically check the supplies of investigational product held by the pharmacist to verify accountability of all investigational product used. The sponsor will verify that a final report of drug accountability to the unit dose level is prepared and maintained in the Pharmacy study file. At the conclusion of the study, all unused investigational product will be destroyed by the pharmacist or returned to the Sponsor after final accountability by the study monitor and agreement of the Sponsor. A certificate of destruction will be provided by the pharmacist to the Sponsor.

At each study visit, the hospital pharmacist will provide the patients with the adequate number of capsules to ensure continuous study treatment until the next visit.

5.8 COMPLIANCE

Administration of the investigational product will be supervised by the investigator. Any delegation of this responsibility must follow *Section* 12.2.

In practice, during study visit days, study nurses will supervise the intake of the appropriate dose of OTX015/MK-8628, explaining to patients the exact number of capsules. They will document the administration, the dose, the time of administration, as well as immediate reaction, if any.

For non-visit days, OTX015/MK-8628 will be taken at home. The patient will notice the number of taken capsules, the time of administration, as well as reaction, if any, including occurrence and time of vomiting, on a specific patient's diary (see Appendix VII; section 16.7).

When a patient will attend a study visit, he/she will bring back to the pharmacist the unused capsules and their diary. According to the center procedures, the diary could be used to fill in the CRF treatment administration part, either directly as Source Document, or as a help for filing in nurse's notes, which will be used as Source Document.

6 PRIOR AND CONCOMITANT ILLNESSES AND TREATMENTS

6.2 PRIOR AND CONCOMITANT MEDICAL CONDITIONS

Additional illnesses, independent of the treated condition, present at the time informed consent is given or within 30 days prior to first study treatment administration must be documented in the section "prior and concomitant conditions" of the CRF. Relevant past illnesses (including other cancers) must also be documented in this section.

Medical conditions first occurring or detected during the study, or worsening of a concomitant illness during the study, are to be regarded as treatment emergent adverse events (TEAEs) and must be documented as such in the section "Adverse Events" of the CRF (see *Section 8.1* of the protocol).

